6.5 POOLING OF CENTRES

No particular analysis is planned.

6.6 HANDLING OF MISSING DATA AND OUTLIERS

Section 7.5 of the CTP describes the handling of missing data.

The original results (OR) approach implies the presentation of data exactly as observed (not using time windows and not setting values to missing).

OR analysis will be performed on parameters and endpoints for which it is not meaningful to apply any imputation rule for the replacement of missing values.

6.6.1 Withdrawals

The reasons for withdrawal from treatment will be reported as indicated on the eCRF.

6.6.2 Efficacy data

Based on the different reasons for patients' data missing for different endpoints, various approaches will be used to assess the impact of missing data on the efficacy endpoints of this trial, depending upon the type of the endpoint. Approaches to be applied are described below.

Missing data imputations will be performed using all available on-treatment data observed up to the respective analysis cut-off date, if applicable.

Some efficacy endpoints are defined in terms of the proportion of patients with a particular binary outcome, i.e. achievement of a GPPGA total score of 0 or 1. Then imputation is planned to take place only at the binary level, i.e., the GPPGA total score itself will not be imputed, but the binary endpoints derived based on these scores will be imputed, unless otherwise specified.

Binary efficacy endpoints for randomized dose at Day 1

The following primary imputation strategy ("NRI") will be performed after the implementation of the estimand concept:

- For endpoints which are measured at multiple visits, if there are available data at the visits both before and after the visit with a missing outcome, then impute as a success only if both neighbouring visits also represent a success (independent of whether the preceding and following observations were selected for analysis based on time windows described in [Section 6.7](#));
- Otherwise, impute as a failure to achieve a response (i.e. no response imputation).

Other imputation schemes will be also considered for the primary and secondary binary efficacy analyses included in the hierarchical testing procedure, including (see the footnote of [Table 6.6.2: 1](#) for the definition of EN):

- Best response imputation (BRI) after implementation of EN: impute all missing values based on the best response observed for the patient at visits prior to withdrawal/occurrence of missing data (independent of whether the observations were selected for analysis based on time windows described in [Section 6.7](#)). If there is no non-

missing data available (including baseline), then the missing value will be imputed as a non-response.

- Exhaustive method (EM) (primary endpoint and key secondary endpoint only) for EN: If fewer than 3 patients have missing data on an endpoint at Week 1 then a list of all possible treatment differences will be generated whereby each of the potential responses (response, non-response) will be imputed for each patient in an exhaustive manner. The primary endpoint analysis will be repeated for each possible combination of imputed values on missing responses and the results will be summarized in a single table.

In addition, the following methods will be implemented to display the data descriptively.

- Observed cases (OC) approach will include all collected data, without imputation for any missing data. Such an OC approach will exclude all values measured after any use of escape medication, or OL Spesolimab use at D8, or rescue medication with Spesolimab.
- Observed cases including intercurrent events (OC-IR) approach is an extension of the OC approach which includes additionally all values which were measured after any use of escape medication, or OL Spesolimab use at D8, or rescue medication with Spesolimab.

With regard to the handling of missing data on the primary and key secondary binary efficacy endpoints at Week 1 and secondary binary efficacy endpoints at Week 4, which are included in the testing strategy, the following table gives an overview of the proposed estimand implementation and missing data imputation methods which are planned to be used.

Table 6.6.2: 1 Handling of estimand and missing data on binary efficacy endpoints in testing strategy

Analysis or display method	Binary efficacy endpoint observed or not	Estimand or display concept		Imputation method on missing data due to other reasons, i.e. withdrew consent, lost to follow up, data not collected, etc.
		[Week 1 and 4] Death, or use of escape medication, or [Week 4 only] OL Spesolimab use at D8 or rescue use with Spesolimab, prior to endpoint	[Week 1 and 4] Use of restricted medication for other purpose	
EN-NRI	Observed/ Not observed	Non-response	Observed	NRI
EN-BRI	Observed/ Not observed	Non-response	Observed	BRI
EN-EM	Observed/ Not observed	Non-response	Observed	EM
EN-PC-NRI	Observed/ Not observed	Non-response	Censored and then imputed by NRI	NRI
OC	Observed	Censored	Observed	n.a.
	Not observed	No imputation	No imputation	No imputation
OC-IR	Observed	Observed	Observed	n.a.
	Not observed	No imputation	No imputation	No imputation

EN: Primary estimand for binary endpoint. For week 1, death or any use of escape medication, and, for week 4, death, or any use of escape medication, or OL Spesolimab use at D8, or any rescue medication with Spesolimab, prior to observing the endpoint(s) is considered to represent a non-response.

EN-PC: Alternative estimand for binary endpoint. For week 1, death or any use of escape medication, and, for week 4, death, or any use of escape medication, or OL Spesolimab use at D8, or any rescue medication with Spesolimab, prior to observing the endpoint(s) is considered to represent a non-response. Any data after the use of restricted medication for other purpose will be censored.

OC = observed cases excluding values after any use of escape medication, or OL Spesolimab use at D8, or any rescue medication with Spesolimab, OC-IR = observed cases including also values after any use of escape medication, or OL Spesolimab use at D8, or any rescue medication with Spesolimab.

"NRI", "BRI" and "EM" (Exhaustive method) mean analyses involving imputed data, cf. [Section 6.6.2](#).

Continuous efficacy endpoints for randomized dose at Day 1

For the primary estimand of continuous endpoints, death or any use of escape medication, or OL Spesolimab at Day 8, or any rescue medication with Spesolimab, prior to observing the endpoint(s) is considered to represent a non-response. Here the outcome of "non-response" itself is not a missing value but is the worst possible outcome of the corresponding

continuous endpoint. See [Section 7.5.2](#) for how to display continuous endpoint with both “non-response” outcome and other numeric continuous values.

The primary imputation strategy of missing values of continuous endpoints is LOCF after the implementation of estimand concept:

- Impute the missing outcome as the last available value (including baseline) prior to the missing outcome;

Wilcoxon rank test on secondary continuous endpoints:

For secondary continuous endpoints, a rank-based approach will be used for testing as below:

The best possible baseline values are the lowest value 0 for Pain VAS score and PSS score, and the highest value 52 for FACIT-Fatigue scale score. The worst possible post-baseline values are the highest values 100 and 16 for Pain VAS score and PSS score respectively, and the lowest value 0 for the FACIT-Fatigue scale score. Therefore, the maximum value for the worst possible change from baseline (i.e., the worst possible post-baseline value – the best possible baseline value) is 100 for Pain VAS, 16 for PSS, and -52 for the FACIT-Fatigue scale. Furthermore, the maximum value for the worst percentage change from baseline in GPPASI at Week 1 and at Week 4 will be the highest observed percentage change from baseline of all patients with non-missing GPPASI at Week 1 or Week 4, which are denoted as PT1 and PT4 respectively.

For Wilcoxon rank tests of the secondary continuous endpoints at week 1 or at week 4, worst case ranks will be assigned to those patients with death, or prior escape medication, or OL Spesolimab at D8, or rescue medication with Spesolimab cf. Section 7.5 of CTP. The ranking rules for the tests are outlined in [Table 6.6.2: 2](#).

Table 6.6.2: 2 Ranking rules for Wilcoxon rank tests of secondary continuous endpoint on EN

	Category	Ranking	Case description	Imputed change from baseline for further ranking score
1	Missing data at week 1/4 ¹ but still alive and no use of either escape medication, OL Spesolimab at D8 or rescue medication with Spesolimab prior to Week 1/4 ¹ .	Rank by imputed value	Patient has available data at visit prior to Week 1/4 ¹	LOCF prior to Week 1/4 ¹
			Patient has no prior available value	102 for Pain VAS 18 for PSS and -54 for FACIT-Fatigue scale PT1/PT4+2 for percentage change from baseline in GPPASI at Week 1/4
2	Use of escape medication, OL Spesolimab at D8 or rescue medication with Spesolimab prior to endpoint collection at Week 1/4 ¹ but still alive.	Rank by OL Spesolimab at D8 or time to rescue medication or time to escape medication from randomized treatment.	Patient has OL Spesolimab at D8, and has no escape medication, and no rescue medication prior to endpoint collection at Week 4	104 for Pain VAS 20 for PSS -56 for FACIT-Fatigue scale PT4+4 for percentage change from baselines in GPPASI at Week 4

Table 6.6.2: 2 Ranking rules for Wilcoxon rank tests of secondary continuous endpoint on EN (cont'd.)

Category	Ranking	Case description	Imputed change from baseline for further ranking score*
		Patient has rescue medication with Spesolimab x days from randomized treatment., and has no escape medication prior to endpoint collection at Week 4 (independent of whether OL Spesolimab was administered at D8 or not)	106-x/1000 for Pain VAS 22-x/1000 for PSS -58+x/1000 for FACIT-Fatigue scale PT4+6-x/1000 for percentage change from baseline in GPPASI at Week 4
		Patient has escape medication y days after randomized treatment and prior to endpoint collection at Week 1/4 ¹ (independent of whether OL Spesolimab was administered at D8 or not, or rescue medication was taken)	108-y/1000 for Pain VAS 24-y/1000 for PSS -60+y/1000 for FACIT-Fatigue scale PT1/4+8-y/1000 for percentage change from baseline in GPPASI at Week 1/4

Table 6.6.2: 2 Ranking rules for Wilcoxon rank tests of secondary continuous endpoint on EN (cont'd.)

	Category	Ranking	Case description	Imputed change from baseline for further ranking score*
3	Patient died before the measurement at Week 1/4 ¹	Ranked by time to death from randomized treatment.	Patient died z days after randomized treatment. (independent of the occurrence of other events)	110- z /1000 for Pain VAS 26- z /1000 for PSS -62+ z /1000 for FACIT-Fatigue scale PT1/4+10- z /1000 for percentage change from baseline in GPPASI at Week 1/4

* Ranked values in this table are only for purpose of rank tests but not for any descriptive displays

¹ For percentage change from baseline in GPPASI at week 1, the imputation rule is based on the data at week 1, but for other secondary continuous endpoints, it is based on the data at week 4.

Other sensitivity analysis of continuous endpoints include an additional estimand (EC) whereby any data after use of escape medication/OL Spesolimab at D8/rescue treatment with Spesolimab will be censored. The following two methods may be used to handle the censored or missing data here:

- A mixed effect model for repeated measurements (MMRM) will be used to handle the missing cases implicitly.
- (For secondary continuous endpoints only) LOCF method will be used to impute the missing cases.

In addition, OC and OC-IR methods will be implemented to display the data descriptively if needed.

With regard to the handling of missing data on the secondary continuous efficacy endpoints at Week 4, which are included in the testing strategy, the following table gives an overview of the proposed estimand implementation and missing data imputation methods which are planned to be used.

Table 6.6.2: 3 Handling of estimand and missing data on continuous efficacy endpoints in testing strategy

[figure not shown]
Analysis or display method	Continuous efficacy endpoint observed or not	Estimand or display concept	Imputation method on missing data due to other reasons, i.e. withdrew consent, lost to follow up, data not collected, etc.
		Death, or use of escape medication, or OL Spesolimab use at D8 or rescue use with Spesolimab, prior to endpoint	
EN-LOCF	Observed/ Not observed	Non-response	LOCF
EC-MMRM	Observed/ Not observed	Censored	MMRM
EC-LOCF	Observed/ Not observed	Censored then imputed by LOCF	LOCF
OC	Observed	Censored	n.a.
	Not observed	No imputation	No imputation
OC-IR	Observed	Observed	n.a.
	Not observed	No imputation	No imputation

[figure not shown]
EN: Primary estimand for continuous endpoint. Death or any use of escape medication or OL Spesolimab use at D8, or any rescue medication with Spesolimab, prior to observing the endpoint(s) is considered to represent a non-response.

EC: Alternative estimand for continuous endpoint. Any data post escape medication use or OL Spesolimab at D8, or rescue medication with OL Spesolimab will be censored.

OC-IR = observed cases including also values after any use of escape medication, or OL Spesolimab use at D8, or any rescue medication with Spesolimab

"LOCF" and "MMRM" mean analyses involving imputed data, cf. [Section 6.6.2](#).

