[figure not shown]
[figure not shown]
[figure not shown]

Clinical Trial Protocol

Document Number:		c15875404-04
EudraCT No.: EU Trial No.:	2017-004231-37	
BI Trial No.:	1368-0013	
BI Investigational Product(s):	Spesolimab (BI 655130)	
Title:	Effisayil™ 1: Multi-center, double-blind, randomized, placebo-controlled, Phase II study to evaluate efficacy, safety and tolerability of a single intravenous dose of BI 655130 in patients with Generalized Pustular Psoriasis (GPP) presenting with an acute flare of moderate to severe intensity	
Lay Title:	A study to test BI 655130 in patients with a flare-up of a skin disease called Generalized Pustular Psoriasis	
Clinical Phase:	II	
Clinical Trial Leader:	

 Phone: [REDACTED]	
Coordinating Investigator:	

 Phone: [REDACTED] Fax: [REDACTED]	
Status:	Final Protocol (Revised Protocol (based on Global Amendment 2)	
Version and Date:	Version: 3.0	Date: 26 Jun 2020
Page 1 of 149		
Proprietary confidential information. © 2020 Boehringer Ingelheim International GmbH or one or more of its affiliated companies. All rights reserved. This document may not - in full or in part - be passed on, reproduced, published or otherwise used without prior written permission.		

CLINICAL TRIAL PROTOCOL SYNOPSIS

Company name	Boehringer Ingelheim
Finished product name	N/A
Active ingredient name:	Spesolimab (BI 655130)
Protocol date	27 June 2018
Revision date	26 Jun 2020
Trial number	1368-0013
Title of trial:	Effisayil™ 1: Multi-center, double-blind, randomized, placebo-controlled, Phase II study to evaluate efficacy, safety and tolerability of a single intravenous dose of BI 655130 in patients with Generalized Pustular Psoriasis (GPP) presenting with an acute flare of moderate to severe intensity
Coordinating Investigator:	 Phone:  ; FAX: 
Trial site(s):	Multi-center trial conducted in 11 to 20 countries.
Clinical phase:	II
Objective(s):	To evaluate efficacy, tolerability and safety of BI 655130 compared to placebo in patients with Generalized Pustular Psoriasis (GPP) presenting with an acute flare of moderate to severe intensity.
Methodology:	Multi-center, placebo-controlled, randomized, double blind
Number of patients entered:	51 patients
Number of patients on each treatment:	34 patients on BI 655130 and 17 patients on placebo

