7.3.1 Primary endpoint analyses

The analysis for the primary endpoint includes the evaluation of patients achieving a GPPGA pustulation subscore of 0 at Week 1.

Any use of escape medication, e.g. use of restricted medication for disease worsening in [Table 4.2.2.1: 1](#), prior to observing the primary endpoint is considered to reflect a failure to achieve the endpoint outcome, i.e. non-response (see primary endpoint definition in [Section 2.1.2](#)).

Due to the small sample size of the trial, an exact statistical test will be used to assess the statistical significance of the treatment effect versus Placebo. Since the traditional Fisher's exact test may be unnecessarily conservative, an alternative test, the Suissa-Shuster Z-pooled test, will be implemented in this trial. The Suissa-Shuster Z-pooled test always preserves the type I error level and is usually more powerful than the Fisher's exact test.

The primary endpoint will be tested, for the RS, using the Suissa-Shuster Z-pooled test at a 1-sided, alpha level of 0.025.

Secondary analysis of the primary endpoint will include:

- A sensitivity analysis utilizing the PPS;
- Analysis of an additional estimand whereby any use of escape medication prior to week 1 will be considered to represent a non-response. For patients who use other restricted medication but not for disease worsening prior to Week 1, data will be censored for further analysis following the use and imputed using the methods described in [Section 7.5](#).
- Sensitivity analyses which utilize alternative methods for the handling of missing data as described in Section 7.5.
- A subgroup assessment according to the Japan vs. non-Japan strata will be assessed descriptively
- Sensitivity analyses to adjust for the covariates, IL36R mutation status (Yes vs. No) and baseline GPPGA total score (3 vs. 4) respectively using logistic regression.

Further analysis of the primary endpoint will include:

- Analysis of the time to first achievement of a response on the primary endpoint via Kaplan-Meier methods.

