7.5 HANDLING OF MISSING DATA

Every effort will be made to collect complete data at all visits. However, missing data will still occur and approaches to handle this are proposed below.

For primary and key secondary and secondary binary endpoints

With regards to the handling of missing data on the primary, key secondary and secondary binary efficacy endpoints, a Non Response Imputation will be applied as the primary imputation approach that is, imputing as a failure to achieve a response, however:

- If there are available data at the visits both before and after the visit with a missing outcome, then impute as a success only if both the preceding and the following

Proprietary confidential information © 2020 Boehringer Ingelheim International GmbH or one or more of its affiliated companies

observations also represent a success and there is no use of escape medication, OL BI 655130 at D8 or rescue medication with BI 655130 within this imputation period;

- Otherwise, impute as a failure to achieve a response (i.e. no response imputation [NRI]).

NRI is a conservative imputation scheme because it assumes that withdrawal (or missing data due to any other reason) is related to treatment failure. Other imputation schemes will therefore be considered for the primary, key secondary and secondary binary efficacy analyses including:

- Best response imputation: impute all missing values based on the best response observed at visits prior to withdrawal/occurrence of missing data. If there is no non-missing data available, then the missing value will be imputed as a failure.
- If fewer than 3 patients have missing data on an endpoint at Week 1 then a list of all possible treatment differences will be generated whereby each of the potential responses (response, non-response) will be imputed for each patient in an exhaustive manner.

For secondary continuous endpoints

For secondary continuous endpoints at Week 4 which are included into the statistical testing strategy, the Wilcoxon rank test will be used.

In test, worst case ranks will be assigned to those with prior escape medication or OL BI 655130 at D8 or rescue medication with BI 655130 or death, and for patients with missing data at Week 4 for other reasons, LOCF method will be used for imputation.

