7.7 DETERMINATION OF SAMPLE SIZE

Based on an application of the defined testing strategy (see [Section 7.2](#)), a simulation based power calculation has been performed for sample size assessment on both the primary and key secondary endpoints. For this purpose, the correlation of the two endpoints is set to be 0.65 which is derived from efficacy data of POC study 1368.11.

The effect of BI 655130 on the proportion of patients achieving a GPPGA pustulation subscore of 0 at Week 1 and separately on the proportion of patients achieving a GPPGA score of (0, 1) at Week 1 will be compared relative to placebo respectively. It is expected that, after one week of treatment with BI 655130, at least 60% of patients will have complete GPPGA pustulation subscore of 0 and at least 60% of patients will have a GPPGA score of 0 or 1. In comparison, only 10% of patients on placebo are expected to have response to each of the primary endpoint and key secondary endpoint at Week 1.

The power estimates below for detecting the clinically relevant differences, for the primary endpoint, the proportion of patients with a GPPGA pustulation subscore of 0 at Week 1 and the key secondary endpoint, a GPPGA score of 0 or 1 at Week 1, were derived using R version 3.3.2, for a sample size of 51 patients (2:1 ratio), and a 1-sided type I error of 0.025. The results are as given in [Table 7.7: 1](#).

Table 7.7: 1

Power to achieve statistical significance for the primary endpoint and key secondary endpoint on BI 655130 versus Placebo under various scenarios for N=51 (2:1)

Sample size: BI 655130 vs. placebo	Primary endpoint/Key secondary endpoint: Proportion of patients achieving GPPGA pustulation subscore of 0 at Week 1 [BI 655130 vs. placebo]/ Proportion of patients achieving GPPGA of (0 or 1) at Week 1 [BI 655130 vs. placebo]	Power (%) to achieve primary endpoint	Power (%) to achieve both primary endpoint and key secondary endpoint
34:17	0.5 vs 0.05/ 0.5 vs 0.05	95.7%	92.9%
34:17	0.55 vs 0.05/ 0.55 vs 0.05	98.1%	96.8%
34:17	0.6 vs 0.05/ 0.6 vs 0.05	99.4%	98.8%
34:17	0.65 vs 0.05/ 0.65 vs 0.05	99.9%	99.7%
34:17	0.5 vs 0.1/ 0.5 vs 0.1	85.3%	78.1%
34:17	0.55 vs 0.1/ 0.55 vs 0.1	92.0%	87.7%
34:17	0.6 vs 0.1/ 0.6 vs 0.1	96.3%	93.9%
34:17	0.65 vs 0.1/ 0.65 vs 0.1	98.5%	97.3%

Note: if the rates of response for both primary endpoint and key secondary endpoint were 0.55 on BI 655130 and 0.1 on placebo, separately, then the overall power to achieve both endpoints would be approx. 87.7%.

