Therefore, with an expected response rate of 0.6 on BI 655130 and 0.1 on placebo for each of the primary endpoint and key secondary endpoint and a type I error of <0.025 (1-sided), for a total sample size of 51 patients, this trial will be able to detect an effect of BI 655130 relative to placebo, for both primary endpoint and key secondary endpoint simultaneously, with an overall power of 93.9%.

8. INFORMED CONSENT, TRIAL RECORDS, DATA PROTECTION, PUBLICATION POLICY, AND ADMINISTRATIVE STRUCTURE

The trial will be carried out in compliance with the protocol, the ethical principles laid down in the Declaration of Helsinki, in accordance with the ICH Harmonized Tripartite Guideline for Good Clinical Practice (GCP), relevant BI Standard Operating Procedures (SOPs), the EU regulation 536/2014, the Japanese GCP regulations (Ministry of Health and Welfare Ordinance No. 28, March 27, 1997) and other relevant regulations.

Standard medical care (prophylactic, diagnostic and therapeutic procedures) remains the responsibility of the patient's treating physician.

The investigator will inform the sponsor immediately of any urgent safety measures taken to protect the trial patients against any immediate hazard, as well as of any serious breaches of the protocol or of ICH GCP, and for Japan, the Japanese GCP regulations (Ministry of Health and Welfare Ordinance No. 28, March 27, 1997).

The Boehringer Ingelheim transparency and publication policy can be found on the following web page: trials.boehringer-ingelheim.com. The rights of the investigator and of the sponsor with regard to publication of the results of this trial are described in the investigator contract. As a rule, no trial results should be published prior to finalization of the Clinical Trial Report.

The certificate of insurance cover is made available to the investigator and the patients, and is stored in the ISF.

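### The exhaustive missing-data check on the Week 1 endpoints stops at three missing patients, and no other listed test counts a missing placebo patient without an observed response as a responder

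*SAP*

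**What the plan says.** Protocol 7.5 and SAP 6.6.2 make non-response imputation (NRI) the main rule for missing binary outcomes. A missing visit is a success only when the visits on both sides of it are successes; for the rest, SAP 6.6.2 says "Otherwise, impute as a failure to achieve a response (i.e. no response imputation").

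Three other inferential approaches to the Week 1 endpoints are listed in SAP Tables 6.3:1 and 6.6.2:1:

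- **EN-BRI**, best response: "impute all missing values based on the best response observed for the patient at visits prior to withdrawal/occurrence of missing data". With no usable data, the patient is a non-responder.
- **EN-PC-NRI**: values after restricted medication taken for another purpose are censored, then imputed by NRI.
- **EN-EM**, the exhaustive method: every missing outcome is set in turn to response and non-response, and the primary analysis is repeated. SAP 6.6.2 opens it with "If fewer than 3 patients have missing data on an endpoint at Week 1 then a list of all possible treatment differences"; Protocol 7.5 has the same condition: "If fewer than 3 patients have missing data on an endpoint at Week 1 then a list of all possible treatment differences will be generated".

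Neither document states the limit by arm or says what happens at three or more. The observed-case displays (OC, OC-IR) are descriptive and impute nothing. The SAP history table records that multiple imputation was removed.

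**The concern.** In a superiority trial, setting a missing placebo patient to non-response lowers the placebo rate and so helps the active arm. A reader will ask how many missing placebo patients would have to be responders before the result fails. Only the exhaustive method answers that, and it is available when one or two outcomes are missing and withdrawn when there are more, which is when the question matters most. With 17 placebo patients, a handful of outcomes can decide the answer.

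The other analyses do not fill the gap. NRI needs two observed successes around the missing visit. BRI needs an earlier observed response, and baseline cannot supply one, because Protocol 3.3.4 requires a GPPGA of at least 3 and a pustulation subscore of at least 2 at treatment start. EN-PC-NRI returns to NRI. The covariate-adjusted logistic regression in SAP 7.4 has no missing-data rule of its own. If the check is then added after unblinding, it becomes a post hoc choice.

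**Working it through.** **Inputs**

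- Test: "using the Suissa-Shuster Z-pooled test at a 1-sided, alpha level of 0.025" (Protocol 7.3.1).
- Size: "34 patients on BI 655130 and 17 patients on placebo" (Protocol synopsis).
- Planning rates: "expected response rate of 0.6 on BI 655130 and 0.1 on placebo" (Protocol 7.7).
- Missing rate q: not given. Assumed at 1%, 2%, 3%, 5% and 8%, equal and independent across arms and unrelated to outcome.

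**Step 1: reproduce the plan's figures.** For x/34 v y/17, Z = (x/34 − y/17) / √[p̄(1 − p̄)(1/34 + 1/17)], with p̄ = (x + y)/51. The exact p is the probability of a Z at least as large, maximised over a grid of common response rates. Power at 0.6 v 0.1 is 96.28% for the primary endpoint (Table 7.7:1: 96.3%). For both endpoints with correlation 0.65, simulation gives 93.9% (stated: 93.9%).

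**Step 2: tipping points.** One-sided p, starting from 2 placebo responders under NRI and adding missing placebo patients as responders:

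| Spesolimab responders | +0 | +1 | +2 | +3 | +4 |
|---|---|---|---|---|---|
| 18/34 | 0.0030 | 0.0109 | 0.0394 | 0.0628 | 0.1841 |
| 19/34 | 0.0021 | 0.0071 | 0.0215 | 0.0624 | 0.1510 |
| 20/34 | 0.0009 | 0.0037 | 0.0110 | 0.0394 | 0.0689 |
| 21/34 | 0.0006 | 0.0022 | 0.0071 | 0.0215 | 0.0624 |

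The planned rates imply 34 × 0.6 = 20.4 and 17 × 0.1 = 1.7 responders. At 20 v 2 the result is lost at three missing placebo patients, the first count at which the method is off.

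Three missing need not all be on placebo. Take 18 v 2, where 18 or fewer of 34 has probability 25% at a 60% rate, with two placebo patients and one spesolimab patient missing. The possible tables are 18 or 19 v 2, 3 or 4: six p-values, from 0.0021 (19 v 2) to 0.0394 (18 v 4), on both sides of 0.025. The plan would not produce them.

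**Step 3: how often the method is off.** The first two columns follow from Binomial(51, q), Binomial(34, q) and Binomial(17, q). The last is simulated at 0.6 v 0.1 (2 million trials per rate). It counts trials that are significant under NRI, have three or more missing, and lose significance when every missing placebo patient is a responder and every missing spesolimab patient a failure.

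| q | 3+ of 51 missing | 3+ missing, at least 1 on placebo | 3+ of 17 placebo missing | Significant result overturned, method off |
|---|---|---|---|---|
| 1% | 1.5% | 1% | 0.1% | 0.15% |
| 2% | 8% | 6% | 0.4% | 0.9% |
| 3% | 20% | 15% | 1.3% | 2.5% |
| 5% | 47% | 37% | 5.0% | 7.4% |
| 8% | 79% | 66% | 15.0% | 17.6% |

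**Step 4: is the cap needed for feasibility?** No. The p-value depends only on responder counts per arm. With k_s spesolimab and k_p placebo patients missing there are (k_s + 1)(k_p + 1) distinct tables: at most 6 for three missing (2 × 3) and 12 for five (3 × 4).

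**The case against.** The strongest reply is that few Week 1 outcomes will be missing.

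- Death and escape medication before the endpoint are already non-response.
- Day 8 is a mandatory visit, the analysis window runs to Day 10 (SAP Table 6.7:1), and open-label drug is offered on Day 8, which gives patients who are still pustular a reason to attend.
- Days 4 to 7 may be skipped only after pustular clearance, so a patient who skips them for that reason already has a primary-endpoint response that BRI counts. A missing patient with no observed response is unlikely to have cleared, given that "only 10% of patients on placebo are expected to have response to each of the primary endpoint and key secondary endpoint at Week 1".
- On average NRI is not lenient. Under equal, non-informative missingness, power at 0.6 v 0.1 falls from 96.3% to 95.5%, 94.8% and 93.8% at 3%, 5% and 8% missing.
- A reader could rebuild the table if responder and missing counts per arm were reported.

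Most of this stands, and it limits how often the gap matters: at 1% to 3% missing, an overturned result goes unexamined in at most about 2.5% of trials. It does not close the gap. The clearance argument is weaker for GPPGA 0 or 1. Low average missingness does not protect a trial in which the losses fall on placebo: with three placebo patients missing and none on spesolimab, the chance of significance is 97.9% under NRI but 64.1% if all three are counted as responders. SAP 7.9 itself says COVID-19 made it harder to keep mandated visits. The exhaustive method is meant as a bound, so an unlikely extreme is no reason to drop it as missing data grow.

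**Conclusion.** The concern holds. In the visible text, once three patients are missing a Week 1 outcome, no listed inferential analysis counts a missing placebo patient without an observed response as a responder. Near the planned result (20/34 v 2/17), significance is lost at three such patients; at 18/34 v 2/17, three missing in total can straddle 0.025.

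This is a gap in a sensitivity analysis and leaves the primary test, estimand and alpha intact. The protocol's description of NRI as conservative can stand for equal, non-informative missingness.

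The conclusion rests on reading the cap as a total over both arms, which is the plain sense but is not spelled out; on the response counts chosen for illustration; and on assumed missing rates. SAP sections 6.4 and 7.6 are not in the public version, but the method tables in 6.3 and 6.6.2 list nothing further for these endpoints.

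**What to change.** Delete the fewer-than-three condition in SAP 6.6.2, and either align Protocol 7.5 or record the departure in SAP section 4. For any number missing, and for both Week 1 endpoints, tabulate the Z-pooled p-value and risk difference for every combination of 0 to k_s imputed responders on spesolimab and 0 to k_p on placebo, and mark where the one-sided p crosses 0.025. If wished, add a sentence that NRI may not be conservative when missingness is informative or concentrated on placebo. Settle this before unblinding.

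The cost is one SAP rule, one protocol alignment or section 4 entry, a short loop in the code, and a somewhat larger table: four spesolimab and two placebo patients missing would give 5 × 3 = 15 rows.
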